## 3 STATISTICAL CONSIDERATIONS

### 3.1 Design Overview

This is a double-blinded, randomized phase 2 trial to evaluate the efficacy and safety of human SARS-CoV-2 immune plasma in individuals who are close contacts to person with COVID-19 within 7 days according to the CDC definition. This will also serve as an internal pilot in the seamless phase 2/3 study.

Eligible participants will be randomized to receive high-titer anti-SARS-CoV-2 immune plasma or control (albumin 5%) in a 2:1 ratio. We plan to enroll a total of 150 participants, with a maximum of 100 receiving the plasma and 50 receiving the control.

Each participant will be followed for 28 days after randomization and treatment, and will be tested and evaluated at baseline and on Days 3, 7, 14, 28 using a seven-category severity scale:

1. Not hospitalized, negative PCR for SARS-CoV-2
2. Not hospitalized, positive PCR for SARS-CoV-2 without symptom
3. Not hospitalized, positive PCR for SARS-CoV-2 with symptoms
4. Non-ICU hospitalization, not requiring supplemental oxygen
5. Non-ICU hospitalization, requiring supplemental oxygen
6. Requiring mechanical ventilation and/or in ICU
7. Death

The primary study endpoint is the rating on Day 28, or last rating evaluated. We will also consider time to various dichotomizations on this scale as secondary

outcomes, including time to death, time to requiring critical care, and time to requiring hospitalization

Other endpoints include:

- Anti-SAR-CoV-2 titers (Days 3, 7, 14, 28, 90 in addition to baseline)
- SAR-CoV-2 PCR positivity (Days 0, 3, 7, 14, 28 in addition to baseline)
- SAR-CoV-2 RNA (Days 0, 3, 7, 14, 28 in addition to baseline)

Exploratory objective:

- To assess the correlation between SARS-CoV-2 PCR positivity from nasal swab specimens, based on RT PCR, and detection of viable SARS-CoV-2 from nasal swab specimens based on viral culture assays

Serious adverse events, and grades  $\geq 3$  adverse events will be monitored during the study period.

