## **1.5. SARS-CoV-2 testing**

The Laboratorio de Pesquisa em DST e AIDS do IPEC/FIOCRUZ (LAPCLIN/AIDS), Laboratório de Virus Respiratórios e Sarampo (IOC/FIOCRUZ) or the Center for Infection and Immunity (CII) laboratory will conduct both a quantitative PCR assay and serologic assay. No clinical decisions will be made based on these results.

For asymptomatic individuals, PCR testing alone will be used for screening. For symptomatic individuals, two swabs will be collected from each potential participant, one for ID NOW (or comparable rapid antigen test) and one for a PCR-based test. The ID NOW test results are available in minutes and will make recruitment more efficient. In view of the high specificity of the ID NOW test (99.7%) (Dinnes, et al., 2021), if either the ID NOW and/or the PCR test results is positive, the individual will be confirmed as SARS-CoV-2 positive.

PCR testing will be conducted for all participants at screening, days 0, 3, 7, 14 and 28 and the viral load will be estimated. Results from the baseline ID NOW COVID-19 or PCR tests will be reported to subjects as SARS-CoV-2 positive or negative. Subsequent PCR results will not be shared with the subjects or the clinical research team in order to reduce bias.

ID NOW COVID-19 assay performed on the ID NOW Instrument is a rapid molecular in vitro diagnostic test utilizing an isothermal nucleic acid amplification technology intended for the qualitative detection of nucleic acid from the SARS-CoV-2 viral RNA in direct nasal, nasopharyngeal or throat swabs from individuals who are suspected

of COVID-19 by their healthcare provider within the first seven days of the onset of symptoms. ID NOW COVID-19 received Emergency Use Authorization from the US FDA in September 2020.

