## 2.3 Study population

### 2.3.1 Inclusion Criteria for Enrollment

1. Subjects must be 18 years of age or older
2. a. Recent close contact3\* with a person with COVID-19, i.e. last close contact occurred within 7 days of anticipated infusion of study product. It is anticipated that most contacts will be household contacts with extensive interaction. All must meet the CDC criteria for close contacts. This includes healthcare workers at higher risk of developing severe disease.  
OR  
b. Recent self-reported or documented evidence of infection by nasal swab ID NOW or PCR that is positive for SARS-CoV-2, i.e., nasal sample was collected within 7 days or 10 days of anticipated infusion of study product for those who are asymptomatic or symptomatic, respectively.
3. Evidence of infection by nasal swab ID NOW or PCR that is positive for SARS-CoV-2 at screening visit

---

 Close contact is defined by CDC as being within approximately 6 feet (2 meters) of a COVID-19 case for a prolonged period of time (without PPE); close contact can occur while caring for, living with, visiting, or sharing a healthcare waiting area or room with a COVID-19 case.

 7 days (if asymptomatic at prescreening) or 10 days (if minimally to moderately symptomatic during prescreening) are based on the number of days from specimen collection date to anticipated infusion date

 A repeat ID NOW and PCR at screening is required for all participants. However, for participants with documented evidence of infection by nasal swab PCR that is positive for SARS-CoV-2 in the prior week, a positive swab is not required to enroll the participant since they were already positive in the past week and will be tested by PCR during the Infusion Visit. At screening, two swabs will be collected from each participant, one for ID NOW (or comparable rapid antigen test) and one for a PCR-based test. If ID NOW is positive, it will not be necessary to wait for the PCR based test result to confirm the positive. If the ID NOW is negative, it will be necessary to wait for the PCR test result: PCR negative will mean individual is not eligible and PCR positive will mean they are potentially eligible if all the other inclusion criteria are met.

4. May or may not be hospitalized
5. No symptoms or no more than 7 days of moderate symptoms at the time of screening.

Moderate symptoms may include:

- a. Moderate rhinorrhea

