**Table: Schedule of Events**

Study period	Screen	Baseline	Infusion	Follow up						
Day	-1 to 0	0	0	1	3±2	7±1	14±3	28±7	60±7	90±7
Eligibility										
Informed consent	x									
Demographic and Medical history	x									
COVID-19 symptom screen	x		x							
SARS-CoV-2 ID NOW and RT-PCR obtained for eligibility	x 									
Pregnancy test 	x									
ABO 	x									
Study Drug Administration										
Randomization		x								
Drug infusion			x							
Study Procedures										
COVID-19 Symptom screen	x		x	x	x	x	x	x	x	
Other symptoms screen	x		x	x	x	x	x	x	x	
Concomitant medications	x		x	x	x	x	x			
Vital signs	x		x 		x	x	x			
Targeted physical examination	x		x			x	x			

 A repeat ID NOW and PCR at screening is required for all participants. However, for participants with documented evidence of infection by nasal swab PCR that is positive for SARS-CoV-2 in the prior week, a positive swab is not required to enroll the participant since they were already positive in the past week and will be tested by PCR during the Infusion Visit. At screening, two swabs will be collected from each participant, one for ID NOW (or comparable rapid antigen test) and one for a PCR-based test. If ID NOW is positive, it will not be necessary to wait for the PCR based test result to confirm the positive. If the ID NOW is negative, it will be necessary to wait for the PCR test result: PCR negative will mean individual is not eligible and PCR positive will mean they are potentially eligible if all the other inclusion criteria are met.

 Urine pregnancy test for women of childbearing potential

 Assessment of ABO type on file; requires two tubes of blood drawn 5 minutes apart, as per NYP Blood Bank procedures

 Vital sign testing: Immediately prior to infusion, 10-20 minutes after start of infusion, at completion of infusion and 15-60 minutes after the end of the infusion

Study period	Screen	Baseline	Infusion	Follow up						
Day	-1 to 0	0	0	1	3±2	7±1	14±3	28±7	60±7	90±7
Assessment of composite outcome of disease severity 			x	x	x	x	x	x	x	
Adverse event monitoring			x	x	x	x	x	x	x	
Laboratory testing										
CBC and CMP 	x					x	x			
SARS-CoV-2 RT-PCR 	x		x		x	x	x	x		
SARS-CoV-2 antibody	x				x	x	x	x		x
Blood for future testing	x				x	x	x	x		
Viral culture 	x				x					

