### 2.3.5 Stratified Randomization

1. Subjects enrolled in the study will be stratified and randomized using an interactive web- based system

 Assessment evaluates whether subject has shifted from “no clinical or laboratory evidence of COVID-19 infection to any of the composite outcomes of disease severity

[figure not shown]
 Comprehensive metabolic panel

 Nasal swab

 Includes sequencing for viral variants

 10 % sample of the nasal swabs

2. Subjects will be stratified by steroid administration (prior oral or IV steroids within prior 2 weeks at time of enrollment or prior inhaled steroids within prior 24 hours at time of enrollment) and by vaccination status (prior COVID-19 vaccine at time of enrollment) and then randomized in a 2:1 ratio to either CP or albumin 5%

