### 4.2 Day -1 to 0 (Screening Visit+)

1. Informed consent (obtained before performing study related activities) and assignment of screening PTID
2. New York Presbyterian Hospital (NYPH) blood transfusion consent (this is the standard procedure for all transfusions of blood products at NYPH)
3. Verification of eligibility (inclusion/exclusion)
4. Locator form
5. Demographics (age, sex ethnicity, race)
6. Medical history (timing of exposure to COVID---19 source patient, acute and chronic medical condition, medications, allergies. Any medical condition arising after randomization and infusion of study product should be recorded as AE)
7. COVID---19 symptom screen (fevers, cough, rhinorrhea, sore throat, diarrhea, shortness of breath, ADLs)
8. Vital signs (pulse, blood pressure, weight, height, temperature, oxygen saturation)
9. Targeted physical examination
10. ID NOW COVID-19 and PCR test to confirm positivity for SARS-CoV-2
11. Laboratory Evaluation
  - SARS-CoV-2 testing (RT-PCR) from nasal swab (10% of the swabs will also be submitted for viral culture).
  - ABO Blood typing (two tubes), CBC, comprehensive metabolic panel
  - Serological testing: anti-SARS CoV-2 titers
  - Blood samples for future studies, including sample for peripheral blood mononuclear cells
  - Urine or serum pregnancy test for females of childbearing potential.

---

 At screening, two swabs will be collected from each participant, one for ID NOW (or comparable rapid antigen test) and one for a PCR-based test. If ID NOW is positive, it will not be necessary to wait for the PCR based test result to confirm the positive. If the ID NOW is negative, it will be necessary to wait for the PCR test result: PCR negative will mean individual is not eligible and PCR positive will mean they are potentially eligible if all the other inclusion criteria are met.

Results from laboratory tests obtained up to 7 days before enrollment may be used for the pregnancy test.

- Volume overload
  - Volume status will be assessed via (1) medical history: history of congestive heart failure and use of heart failure medications; and (2) physical exam: vital signs, lung exam, assessment for peripheral edema.
  - Enrollment will be deferred for patients who have active volume overload in order to avoid cardiovascular decompensation from the receipt of additional volume. Once the patient's volume status has improved, enrollment may then proceed. [note this is not an exclusion]

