#### **5.2 Virologic measures**

- Rates and duration of SARS-CoV-2 PCR positivity (RT PCR) at days 0, 3, 7, 14 and 28
- Peak quantity levels of SARS-CoV-2 RNA at days 0, 3, 7, 14 and 28
- Culture positivity at baseline and at day 7 in a subset of specimens
- Correlation between viral culture positivity and PCR positivity for SARS-CoV-2

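### The exploratory culture objective relies on yes/no PCR status in about 15 swabs per visit, so its correlation is likely to be imprecise and sometimes not computable; RNA level on the same swabs would serve it better

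*Combined protocol and SAP*

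**What the plan says.** The objective appears in the Protocol Summary, Section 2.1.4 and Section 3.1, where it reads "To assess the correlation between SARS-CoV-2 PCR positivity from nasal swab specimens, based on RT PCR, and detection of viable SARS-CoV-2". Section 5.2 lists the matching measure as "Correlation between viral culture positivity and PCR positivity for SARS-CoV-2". In each place both variables are yes/no.

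The culture sample is small. Section 4.2 says that "10% of the swabs will also be submitted for viral culture" at screening, and footnote 17 to the Schedule of Events describes a "10 % sample of the nasal swabs". Section 3.1 sets the trial's size: "We plan to enroll a total of 150 participants".

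The visits do not agree. The "Viral culture" row of the Schedule of Events is marked at Screen and Day 3±2, while Section 5.2 places culture at baseline and Day 7. The visit lists in 4.5 and 4.6 do not mention culture, so they do not settle it.

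Entry selects on a positive test. Inclusion criterion 3 in Section 2.3.1 requires "Evidence of infection by nasal swab ID NOW or PCR that is positive for SARS-CoV-2 at screening visit". Its footnote 5 waives the positive screening swab for people with a documented positive PCR in the preceding week.

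RNA quantity is available. Section 1.5 says of the PCR tests at screening and on days 0, 3, 7, 14 and 28 that "the viral load will be estimated". Elsewhere RNA level is used only to compare the arms; it is not linked to culture. Section 3.2 names no method for the culture objective.

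**The concern.** A correlation needs variation in both variables. Here one of them is reduced to positive or negative and then observed in a small subset of people chosen because they tested positive, at screening and at an early follow-up visit. If few or none of the cultured swabs are PCR negative, the estimate is either very imprecise or does not exist.

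Even when it can be computed, the yes/no comparison addresses the less useful question. The practical interest in culture is to learn which PCR-positive swabs contain viable virus, and an analysis that treats all PCR-positive swabs alike cannot show that. What is at stake is the yield of the culture work and the one exploratory objective. The go/no-go decision, the secondary comparisons of the arms and the safety analyses do not depend on it.

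**Working it through.** The plan states no sample size, precision or power for this objective, so there is no figure of its own to reproduce.

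**Inputs.** Enrolment of 150 (Section 3.1) and a culture fraction of 10% (Section 4.2; footnote 17 to the Schedule of Events). The PCR-positive share p at the cultured visits is not given, so a range of 80% to 95% is assumed.

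**Number of swabs.** 0.10 × 150 = 15 per visit, or 30 over two visits, if the sample comes from enrolled participants.

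**Chance of no or almost no PCR-negative swab.** With independent swabs and n swabs in all, P(no negative) = pⁿ and P(at most one negative) = pⁿ + n(1 − p)pⁿ⁻¹. For example, at p = 0.90 and n = 15: 0.90¹⁵ = 0.206, and 0.206 + 15 × 0.10 × 0.90¹⁴ = 0.206 + 0.343 = 0.549.

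| p (assumed) | Expected negatives in 15 | P(none in 15) | P(at most one in 15) | P(none in 30) |
|---|---|---|---|---|
| 80% | 3.0 | 0.035 | 0.167 | 0.001 |
| 90% | 1.5 | 0.206 | 0.549 | 0.042 |
| 95% | 0.75 | 0.463 | 0.829 | 0.215 |

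The 30-swab column takes the same share at both visits.

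**Best case with one negative.** If 1 of 15 swabs is PCR negative, the most extreme table has all 14 PCR-positive swabs growing virus and the single negative not growing it. Its probability is 1/15 = 0.067, which is the smallest two-sided Fisher p attainable.

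**Simulated power of the yes/no comparison** (two-sided Fisher test at 0.05, no PCR-negative swab grows virus, 4,000 runs each). Entries are for culture yields of 30% / 50% / 70% among PCR-positive swabs, all assumed.

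| p | 15 swabs | 30 swabs |
|---|---|---|
| 80% | 0.01 / 0.11 / 0.39 | 0.05 / 0.45 / 0.91 |
| 90% | 0.00 / 0.02 / 0.11 | 0.00 / 0.11 / 0.48 |
| 95% | 0.00 / 0.00 / 0.03 | 0.00 / 0.02 / 0.16 |

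**RNA level instead.** Assume that half the swabs are culture positive, that swabs are independent and that RNA is normally distributed on the analysis scale. A two-sided Mann-Whitney test of RNA level by culture result then has power 0.47 / 0.65 / 0.84 with 15 swabs and 0.85 / 0.96 / 0.995 with 30, at AUC 0.80 / 0.85 / 0.90. The AUC values are assumptions and the model differs from that of the Fisher calculation. The two sets show the order of difference, not an exact gain. Repeated swabs from one participant would carry less information than independent ones.

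**If screen-failure swabs are sampled.** Let a share s of those screened be PCR-negative failures, with all enrolled participants PCR positive. Screened = 150/(1 − s), cultured = 10% of that, and negatives = s × cultured. For s = 10%, 20% or 30% (assumed), 167, 188 or 214 are screened, 16.7, 18.8 or 21.4 are cultured, and 1.7, 3.8 or 6.4 of these are negative.

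**The case against.** A reader might infer that eligibility makes almost every cultured swab PCR positive, so that the correlation is undefined and the objective cannot be answered at all. The documents do not support that, for four reasons.

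- No entry rule fixes PCR status after enrolment.
- At screening, a positive ID NOW alone satisfies criterion 3, and the prior-week exception admits people whose screening swab is negative.
- The 10% is of swabs, and screening swabs are taken before eligibility is settled; footnote 18 in Section 4.2 describes people who prove PCR negative and are then ineligible. Their swabs may be among those cultured.
- If Section 5.2 is right and the follow-up culture is at Day 7, more negatives are plausible. With 30% negative (assumption), 15 × 0.30 = 4.5 are expected and the chance of none is 0.70¹⁵ = 0.005.

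All four stand. They turn a certainty into a risk whose size depends on a share that the plan does not give.

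It can also be said that culture yield among PCR-positive swabs could be reported with a confidence interval even if no swab were negative, and that Section 3.2 leaves the final statistical analysis plan to be settled before unblinding. Both are true. The first is a different quantity from the stated objective. The second means that the gap can still be closed; it does not show that it has been. The current text names neither a method nor a link between culture and RNA level.

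**Conclusion.** The point holds as a minor one. The objective pairs culture with binary PCR status in a 10% subset, about 15 swabs per visit, where selection on a positive test is likely to leave few PCR-negative swabs. Under assumed positive shares of 80% to 95%, the correlation cannot be computed in 4% to 46% of cases per visit, or 0.1% to 22% with two visits pooled. When it can be computed it is likely to be imprecise; at 80% positive with 30 swabs, power still runs from 0.05 to 0.91 depending on an unknown culture yield. In no case does it show which PCR-positive swabs carry viable virus.

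These figures rest on independent swabs, on sampling from the 150 enrolled, and on shares that are not in the documents. They do not show that the correlation must be undefined or that the culture work is wasted. The preference for RNA level does not rest on the exact share: viral load is already to be estimated, and it keeps information that the yes/no split discards.

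**What to change.** - In 2.1.4, 3.1 and 5.2, and in the matching line of the Protocol Summary, state the analysis as culture result against quantitative SARS-CoV-2 RNA level on the same swabs. Use logistic regression or an ROC curve with a confidence interval, allowing for repeated swabs from one participant.
- Keep the cross-tabulation of culture by PCR positivity as a descriptive table.
- State whether the 10% sample includes swabs from screen failures.
- Reconcile the culture visits: Screen and Day 3 in the Schedule of Events, baseline and Day 7 in Section 5.2.

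The cost is wording. The number of cultures stays the same and no further measurement is needed. The method can go into the final statistical analysis plan that Section 3.2 promises before unblinding.

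Choosing swabs across RNA bands, or culturing at later visits, would give a better spread but is optional. The first needs RNA results before swabs are picked for culture, and the second changes the Schedule of Events.

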## 3.2 Statistical Analysis

Primary Analysis and go/no-go decision: The severity scale of the two groups will be compared using stratified, Mann Whitney test. Specifically, a one-sided  $P < 0.15$  favoring the immune plasma arm will constitute a “go decision” in this phase 2 trial, suggesting evidence of promise for further investigation in an expanded Phase 3 study. The results in this trial will then be used to plan the Phase 3 sample size, with possibility that the data in this Phase 2 trial will be included in the final analysis using adjusted  $P$  values. Details of sample size re-estimation and adjusted analysis, as well as the final statistical analysis plan, will be determined before unblinding the study data.

This analysis will be intent-to-treat. Given the short study duration and the nature of the treatment, however, we anticipate minimal non-compliance and loss to follow-up.

Subgroup Analysis: If the stratified analysis reaches the go decision, with  $P < 0.15$ , we will explore the treatment effect within each stratum using Mann Whitney test.

Secondary Analyses: All secondary efficacy analyses will be intent-to-treat. Time-to-event variables (e.g. time to death) will be analyzed using Cox proportional hazard model. Longitudinal data collected over multiple days (e.g., PCR positivity) will be analyzed using generalized linear mixed models. Treatment effects on these variables will be estimated with 95% confidence intervals.

Safety Analyses: Serious adverse events will be summarized by grades and types using proportions and 95% confidence intervals for the two study arms, and the two arms will be compared using Fisher's exact test.

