## PROTOCOL SUMMARY:

**Long title:** A Phase 2 Randomized, Double-blinded Trial to Evaluate the Efficacy and Safety of Human Anti- SARS-CoV-2 Plasma for Early Treatment of COVID-19

**Short title:** Convalescent Plasma for Early Treatment of COVID-19

**Clinical Phase:** 2

**IND Sponsor:** [name]

**Principal Investigator:** [name]

**Conducted by:** Columbia University

**Sample Size:** SARS-CoV-2 positive nasal swab at baseline: 150 subjects

**Study Population:** High risk for severe COVID-19 case who are 18 years of age or older and SARS-CoV-2 positive and asymptomatic or mildly to moderately symptomatic at baseline.

**Study Duration:** Accrual will take 4-6 months to complete and subjects will be followed for 90 days after enrollment.

**Study Design:** Double-blinded, randomized control trial to assess the efficacy and safety of anti-SARS-CoV-2 convalescent plasma as early treatment. Participants will be randomized 2:1 to receive either convalescent plasma qualitatively positive for SARS-CoV-2 antibody ("anti-SARS-CoV-2 plasma") or control (albumin 5%).

**Study Locations:** National Institute of Infectious Diseases Evandro Chagas (INI) at Oswaldo Cruz Foundation (Instituto Nacional de Infectologia Evandro Chagas-FIOCRUZ (INI-FIOCRUZ) ([name]); Laboratorio de Pesquisa em DST e AIDS do IPEC/FIOCRUZ (LAPCLIN/AIDS) ([name]); Laboratório Central do Instituto Nacional de Infectologia Evandro Chagas ([name]); Laboratório de Virus Respiratórios e Sarampo (IOC/FIOCRUZ) ([name]); Laboratório Richet de Pesquisa e Fisiopatologia Humana Ltda ([name]); Agência Transfusional - Laboratório Central INI ([name]);

---

 See Section 2.3.1 for definition of high risk

Center for Infection and Immunity ([name]).

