- b. Moderate sore throat or throat irritation
- c. Moderate cough
- d. Moderate fatigue (may interfere with ability to perform ADLs)
- e. Moderate chills, measured temperature and/or feeling feverish, muscle pain

6. Calculated Risk Score for severe COVID-19 [based on CDC description] of 0 points if on supplemental oxygen at enrollment; otherwise Calculated Risk Score of  $\geq 1$ .
  - Age 65-74: 1 point
  - Age  $\geq 75$ : 2 points
  - Known cardiovascular disease (including hypertension): 1 point
  - Diabetes mellitus: 1 point
  - Pulmonary disease (COPD, moderate to severe asthma, current smoking or other): 1 point
  - Morbid obesity: 1 point
  - Immunocompromised state: 1 point  
Received a bone marrow or solid organ transplant at any time, received chemotherapy for a malignancy within the past 6 months, has an acquired or congenital immunodeficiency, currently receiving immunosuppressive or immune modulating medications, HIV with non-suppressed viral load and/or CD4+ T cell count  $<200$  cells/mL).
7. Those who do not require more than 4 LPM of supplemental oxygen at enrollment.

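### Inpatients and patients on oxygen may enrol, but the go/no-go test does not use clinical status at entry: a cheap gain in precision, with strata wording and one risk set to tidy

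*Combined protocol and SAP*

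**What the plan says.** **Who enters.** Inclusion criterion 4 in Section 2.3.1 reads "May or may not be hospitalized". Criterion 7 admits "Those who do not require more than 4 LPM of supplemental oxygen at enrollment", and criterion 6 sets the risk score at "0 points if on supplemental oxygen at enrollment; otherwise Calculated Risk Score of" 1 or more. Infection is required: the Protocol Summary gives the sample as "SARS-CoV-2 positive nasal swab at baseline: 150 subjects", and criterion 3 asks for "Evidence of infection by nasal swab ID NOW or PCR that is positive for SARS-CoV-2 at screening visit". Footnote 5 waives the positive screening swab after a documented positive PCR in the prior week.

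**Outcome.** The primary endpoint is the seven-category rating at Day 28 or the last rating. Category 4 is non-ICU hospitalisation without oxygen and category 5 is the same with oxygen.

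**Primary test.** Section 3.2: "The severity scale of the two groups will be compared using stratified, Mann Whitney test", with a go decision at one-sided P < 0.15. It names no strata or covariates. It defers the final SAP to a date before unblinding.

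**Strata elsewhere.** Section 2.3.5: "Subjects will be stratified by steroid administration", and also by prior vaccination, which makes up to four cells. Section 3.3 speaks of two strata and labels them by infection status.

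**Entry status.** Section 3.1 has participants rated on the scale at baseline. The Schedule of Events first marks "Assessment of composite outcome of disease severity" at the infusion visit. Footnote 13 to that row describes a shift from a start state with no evidence of infection.

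**Time to event.** Section 3.1 lists time to requiring hospitalisation among the secondary outcomes and Section 3.2 assigns a Cox model. Neither covers participants already in hospital.

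**The concern.** A participant enrolled as an inpatient is already in category 4, or in category 5 if on oxygen, of the scale that decides go or no-go. Entry status is therefore an earlier value of the outcome itself, and the plan gives it no role. Leaving out a prognostic baseline value costs power and leaves a single 100:50 allocation exposed to chance imbalance in the number of such patients.

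Two gaps in wording go with this. The strata of the primary test have to be inferred, and the two places to infer them from disagree. The text also does not say how an inpatient at entry is handled in time to hospitalisation.

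**Working it through.** **1. The plan's own power.** Inputs: 100 v 50, odds ratio 2, one-sided 0.15 (z = 1.036), Table 2. The Whitehead formula is power = Φ(ln 2 × √V − 1.036), with V = [100 × 50 × 150 / (3 × 151²)] × (1 − Σp³) = 10.964 × (1 − Σp³), where p is the 2:1 average of the plasma and control columns.

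- Scenario 1: p = 0.78, 0.08, 0.073, 0.037, 0.03. So 1 − Σp³ = 0.524, V = 5.75, power = Φ(1.662 − 1.036) = 73%.
- Scenario 2: p = 0.70, 0.22, 0.027, 0.027, 0.013, 0.013. So 1 − Σp³ = 0.646, V = 7.09, power = Φ(1.845 − 1.036) = 79%.

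Simulation of the tie-corrected test (200,000 trials per setting) gives 74.2% in Scenario 1 with no strata, 74.2% with two and 74.1% with four. Scenario 2 gives 80.8%, 80.9% and 80.9%. False-go is 15.1% and 15.0%. The stated 74% and 80% therefore reproduce. With identical distributions across strata, the number of strata does not move them.

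**2. Adding entry status.** The documents do not give these inputs, so they are assumed:

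- the share of participants hospitalised or on oxygen at entry;
- the odds ratio (OR) of that status for a worse Day 28 rating;
- treatment odds ratio 2 within each entry group, with the mixture of the two groups fixed to the Table 2 control column;
- 50% vaccinated;
- steroid use either 30% in everyone, or 70% of hospitalised/oxygen patients and 15% of the rest.

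Trials use 2:1 blocks of 6 within steroid × vaccination. The comparison is the van Elteren test on those four cells against the same test with one added hospitalised/oxygen stratum, which takes those patients out of the four cells. Change in go power, in percentage points over both scenarios:

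| Share | OR 3 | OR 6 |
|---|---|---|
| 3% | 0 to +0.1 | +0.3 to +0.6 |
| 5% | 0 to +0.2 | about +1.1 |
| 10% | +0.2 to +0.6 | +1.8 to +2.2 |
| 20% | +0.7 to +1.3 | +2.8 to +4.0 |

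The 3% and 5% rows use the 70%/15% steroid split only. At OR 1 (10-20% share) the change is −0.5 to −0.1. At 10-20% shares the four-cell test has power of 73-74% (Scenario 1) and 78-79% (Scenario 2) at OR 3, and 69-72% and 74-77% at OR 6. Average false-go is 15% for both tests.

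**3. Chance imbalance.** The SD of the between-arm difference in share is √[f(1 − f)(1/100 + 1/50)]. For f = 0.20 it is √(0.16 × 0.03) = 6.9 points, so a gap of 10 points or more arises in about 15% of trials. For f = 0.10 it is 5.2 points, and about 5%.

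**4. Strata wording.** Section 2.3.5 gives two factors and up to four cells. Section 3.3 gives two strata, infected and non-infected. Every participant needs a positive test at screening or a documented positive PCR in the prior week, so a non-infected stratum has no members by design. Footnote 13's start state fails for the same reason.

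**5. Time to hospitalisation.** There are three possible codings for inpatients at entry. Excluding them leaves a randomised comparison in those at risk. Keeping them event-free only enlarges both risk sets in about the 2:1 ratio. Counting them as day-0 events adds events in the null ratio: at a 20% share, 150 × 0.20 = 30 events, about 20 v 10, which pulls the hazard ratio towards 1. With a true hazard ratio of 0.50 and an assumed 28-day risk of first admission of 50-60%, that coding gives a median of about 0.65 at a 20% share and 0.58 at 10%.

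**The case against.** The strongest reply is that nothing here is broken. Randomisation keeps the test at its level, the stated power is right, and Section 3.2 leaves the final SAP open until unblinding. Entry is limited to moderate symptoms or less, and the logistics (site screening visits, home follow-up visits, single-occupancy transport) suggest mainly outpatients, so the share may be below 10% and the gain close to nil. Footnote 5 also lets some participants enter PCR-negative, so entry status varies across categories 1 to 3 as well. All of this stands, and it is why the point is rated as a precision gain.

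Four stronger readings are tempting, and the documents do not support them.

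- A reader might infer that the go rule is biased. At an assumed 20% share, an 8-12 point excess of these patients in control does raise false-go to 23% (OR 3) or 28-29% (OR 6). But that excess occurs in about 7-8.5% of trials, the mirror-image excess in plasma lowers it to 8-9% or 5%, and the average is 15%. The same holds for any omitted prognostic factor.
- A reader might infer that the strata mismatch undermines the power figures. It does not change them.
- A reader might infer that the hazard ratio for hospitalisation will be diluted. Only day-0 event coding does that materially, and no section proposes it.
- A reader might sum Table 2's control categories 4 to 7 to 30% and 12% and treat these as risks of admission. They describe status at Day 28 or last rating. They miss patients admitted and discharged earlier, and would include entry inpatients who are still in hospital.

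**Conclusion.** The point holds as a low-cost improvement. Entry status lies on the outcome scale, should be obtainable from the enrolment record and is unused. On the assumed values, using it is worth about 0 points of go power at a 5% share with OR 3, up to about 1 point at 10-20% with OR 3, and about 2 to 4 points at 10-20% with OR 6, against a loss of up to 0.5 points if it carries no prognosis. The share and the odds ratio are assumptions, and the size depends wholly on them. The test is valid and the stated power is correct.

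The unnamed strata and the missing risk-set rule are gaps in specification. They do not depend on those assumptions and should be closed in any case.

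**What to change.** 1. **Section 3.2.** Specify a single primary test: van Elteren, with steroid × vaccination strata among participants neither hospitalised nor on oxygen at randomisation, plus one stratum for those hospitalised or on oxygen. Fix the collapsing rule before unblinding. Take entry status from the record at or before randomisation. Do not use the infusion-visit rating, because Section 2.5 lets infusion follow randomisation by up to 48 hours. Keep the exploratory within-stratum analyses to the Section 2.3.5 factors: at a 10% share the added stratum is about 10 v 5 patients.
2. **Section 3.3 and footnote 13.** Replace the two-strata and infection-status wording, and the uninfected start state, so that they match Section 2.3.5 and the infected population. The stated power does not change.
3. **Time to requiring hospitalization.** State that participants hospitalised at randomisation are not counted as day-0 events, and define the analysis among those not hospitalised at randomisation. Note that this is a baseline-defined subset of the intent-to-treat population, since Section 3.2 makes all secondary efficacy analyses intent-to-treat.

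The cost is text, plus a check that hospital status at enrolment is a recorded field (oxygen status is already needed for eligibility). Five strata leave on average 0.3 patients or fewer in strata with only one arm. Crossing fully to eight strata leaves 1.5 to 2.9 and can lose 0.6 points at OR 3, so the single added stratum is preferable. The hospitalisation analysis uses fewer patients.
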